4.1 Study Objectives

PRIMARY OBJECTIVE(S)

1. Evaluate the impact of the intervention on the diagnosis of SND
2. Evaluate the impact of the intervention on SND subjects that receive an indicated IPG device

SECONDARY OBJECTIVES

The key secondary objectives with pre-specified hypotheses to be tested include:

1. Describe the diagnosis and treatment of Phase I subjects
2. Evaluate the change in time to diagnosis of SND before and after intervention
3. Evaluate the change in the time to receiving an indicated IPG device for SND subjects before and after intervention
4. Evaluate the caregiver burden between pre-implant and 6 months post-implant
5. Evaluate change in Quality of Life (QOL) and functional status between pre-implant and 6 months post-implant

4.2 Subject Selection

Subjects of both genders meeting all the inclusion criteria and none of the exclusion criteria are eligible for the study.

Inclusion Criteria:

- Patient is at least 18 years of age
- Patient's heart rate meets at least **one** of the following:
 - Patient has a sinus rate ≤ 50 **OR** a junctional escape rhythm no faster than 50
 - Patient has a history of exercise intolerance
- Patient complains of general fatigue, shortness of breath, shortness of breath with exertion, syncope, light headed dizziness, palpitations, lethargy, dyspnea **OR** malaise within the last 30 days that are not related to other discovered causes (such as untreated hypothyroidism or anemia).
- Patient (or patient's legally authorized representative) is willing and able to sign and date written Patient Consent Form/Patient Data Release Consent

[figure not shown]
Exclusion Criteria:

- Patient has type II 2nd degree AV block, High degree AV block (2:1, 3:1, 4:1 etc.) or 3rd degree AV block
- Patient has recent history of blood loss
- Patient has a medical history leading to suspicion of neurological disorder
- Patient has a history of Chronic Atrial Fibrillation
- Patient is enrolled or planning to participate in a concurrent drug and/or device study at any time during the course of this clinical study without documented pre-approval from the Medtronic study manager
- Patient is not expected to survive for 12 months
- Patient is anticipated to be unwilling or unable to comply with the clinical investigation plan

Subjects will be screened to ensure they meet all of the inclusion and none of the exclusion criteria. Subjects are considered enrolled upon signing the Informed Consent Form/Patient Data Release.

4.3 Study Design

There are two phases to IMPROVE Brady:

Phase I: This phase of the study serves as a control period. During Phase I physicians will assess and treat subjects per their site's standard care practice. Enrollment for Phase I is anticipated to occur for approximately 12 months but will continue until 550 subjects have been enrolled for the geography/country. For subjects enrolled during Phase I, collection of diagnostic assessment and implant data will be complete 6 months after the last enrollment for the geography/country. At that time, all Phase I subjects will be exited.

If a center becomes active after the geography/country enrollment goal for Phase I has been met or the center did not enroll at least 10 subjects before Phase I enrollment stopped then the center will enroll Phase I subjects until 10 subjects have been enrolled at that center. Once 10 subjects have been enrolled at the center, enrollment will stop and the subjects will be followed for a maximum of 6 months and exited from the study.

Phase II:

The objective of the IMPROVE Brady study is to provide investigators with comprehensive resources that may be adapted by the Principal Investigator and his/her colleagues to create a practice specific process improvement intervention to improve the quality of care for patients.

At the completion of Phase I, the Principal Investigator and co-investigators will complete an educational workshop and be given access to the IMPROVE Brady toolkit. In addition, the Principal Investigator and his/her colleagues are encouraged to adapt tools from the IMPROVE Brady toolkit to create a practice specific process improvement intervention.

Immediately following completion of the educational workshop, study investigators will receive written authorization from Medtronic that they are authorized to enroll subjects in Phase II. Enrollment during this phase is anticipated to occur for approximately 18 months per geography/country.

[figure not shown]
The IMPROVE Brady process improvement intervention toolkit may include an education workshop, diagnostic algorithm(s), patient video and tools for investigators to educate their patients on their disease state, available therapy options, and benefits and risks associated with the therapy options.

During Phase II a patient survey assessing the subject's quality of life and functional status, will be completed by subjects meeting an SND indication for pacing therapy and being implanted with a market released pacemaker from the Medtronic family of devices. The patient survey must be completed before the implant procedure and again at 6 months post-implant.

The caregiver of the subject being implanted with the market released pacemaker from the Medtronic family of devices will be asked to participate in a caregiver survey. The purpose of the survey is to assess how providing care to the person receiving the pacemaker impacts the caregiver. Prior to completing the survey an Informed Consent or Patient Data Release will need to be signed by the caregiver. The caregiver survey will be completed prior to the implant procedure and again at 6 months post-implant. The same caregiver must complete the pre and post implant surveys of the same patient.

For subjects enrolled during Phase II collection of diagnostic assessment data will be complete 6 months after last enrollment for the geography/country. At that time, any subjects without a diagnosis will be exited from the study. Collection of implant data will be complete 6 months after the last Phase II diagnosis for the respective geography/country. Any subjects not implanted by the end of the 6 months will be exited from the study. The Geography/country study timeline (Figure 2) depicts the geography/country timeline.

Figure 2: Geography/country study timeline

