4.1.2. Primary Objective #2

Evaluate the impact of the intervention on SND subjects receiving an indicated IPG device.

This document is electronically controlled. Printed copies are considered uncontrolled.

Confidential

4.1.2.1. *Endpoint Definition*

The absolute change in the proportion of subjects receiving indicated therapy at pre-specified time points (% = number receiving IPG/number with SND diagnosis x 100 at time point t where t= 3, 6, and any additional 3-month interval for which there is sufficient follow-up information) and the absolute change in the number of subjects implanted per person-year.

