5. Subject has completed the final scheduled follow-up visit (in Phase II).

This document is electronically controlled. Printed copies are considered uncontrolled.

Confidential

6. Geography/country completion of Phase I follow-up
7. Study closure

The IMPROVE Brady study will not use randomization to divide subjects into treatment groups, but rather will implement a two-phase design. Since the current rates of SND diagnosis and IPG therapy are not known, it is not feasible to construct a study with two simultaneous treatment arms and adequately power the comparison. Thus, the IMPROVE Brady study will have two sequential phases. In the first phase, the control phase, we expect to obtain baseline measurements for key variables including the rate of SND diagnosis and the rate of implantation of an IPG in subjects with an SND diagnosis. Once phase one enrollment is complete for a geographic region, patients will be followed for six months and then will be exited from the study. Physicians at participating centers will then receive an educational intervention and comprehensive disease state management tools on the adoption of ACC/AHA/HRS and ESC indications. In the second phase, the experimental phase, patients will have scheduled follow-up to collect questionnaire data if they are implanted with an IPG manufactured by Medtronic.

Each of the geographies currently participating has differing rates of SND diagnosis and implantation. Early enrollment figures anticipate the accrual of 60 subjects per month per geography, to be obtained through ten or more clinical centers. Given that baseline disease and treatment rates differ by geography, we anticipate that statistical analysis will stratify by geography and thus sample size calculations shall be stratified also. It may also be necessary to look more finely at rates by site within geography. All primary and secondary objectives will be investigated within each geography, in addition to the overall testing of primary and secondary objectives, which will include geography as a covariate.

Baseline IPG Rates

Table 1 shows WHO estimates of new implantation rates per million people (Mond *et al*)

Table 1

Region	Country	Centers	New Implants/Million (2005)
Eastern Europe	Russia	99	101
Asia	China	417	13
	Hongkong	20	157
	South Korea	100	29
	Taiwan	78	119
Southeast Asia	India	417	7
	Singapore	10	91
	Thailand	46	22

This document is electronically controlled. Printed copies are considered uncontrolled.

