8.5.2.1. Analysis Methods

A. Statistical Methodology

To compare the proportion of subjects that receive indicated therapy pre-intervention (Phase I) to the proportion post-intervention (Phase II), a Fisher's Exact test will determine statistical significance. A Fisher's exact test is recommended for smaller sample sizes. The proportion of subjects diagnosed will be evaluated at multiple time points because the time from diagnosis to implant is expected to vary by geography. Shorter time intervals will be used to evaluate the proportion of implants than for the proportion of diagnosis because time from diagnosis to implant is typically shorter than the time from enrollment to SND diagnosis. Thus, times are pre-specified starting at 3 months and any additional 3-month interval thereafter for which there is sufficient follow-up data available to compare study phases. Proportions calculated at all available time points will be reported. Additionally, a Poisson regression will compare the average number of subjects with an implant where the subject time in study beginning at the time of SND diagnosis is treated as an offset in the model. The above described tests will be performed only for the South Asia geography as described in Section 6. Further, similar tests will compare the differences in the types of therapy received in Phase I and Phase II. For example, a Fisher's exact test will compare the frequency of dual chamber device use pre- and post-intervention.

This document is electronically controlled. Printed copies are considered uncontrolled.

Confidential

B. Determination of Patients/Data for Analysis

Subjects that meet inclusion criteria and obtain an SND diagnosis shall be included in this analysis. The proportion estimates will be calculated based on information from fixed time points at 3 months of follow-up, 6 months of follow-up, and any additional 3-month interval thereafter for which there is sufficient follow-up data available to compare study phases. The number of subjects that obtain an IPG by pre-specified time point $t = 3, 6, \text{ etc.}$, will be included in the numerator and the number of subjects with an SND diagnosis will be included in the denominator.

C. Additional Analyses

- In addition to the overall diagnosis and treatment rates between Phase I and Phase II, various descriptive summaries of the subjects will be explored by geography, including the following:

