8.5.2.2. Sample Size Methods and Assumptions

The proportion of IPG therapy in SND subjects is currently unknown within the study geographies. The PANARM HF study of 2000 subjects found that 146 out of 331 bradycardia subjects (44%) had symptomatic SND and that 15 (10%) of SND subjects opted for IPG therapy. PANARM HF included symptomatic HF which is different than the IMPROVE Brady population. Thus, the percentages expected in IMPROVE Brady may differ from those observed in PANARM HF. Assuming that 20% of subjects will be diagnosed with SND, this suggests that there will be 100 SND subjects in Phase I and 200 in Phase II per geography/country. Further assuming that IPG therapy will be adopted by 10% of SND subjects at three months after diagnosis, or equivalently an IPG incidence of 0.25 diagnoses per person-year, this means that the margin of error will be $\pm 8.0\%$ in a sample of 100 subjects per geography/country, based on a 95% confidence interval. If there are 100 SND subjects in Phase I and 200 SND subjects in Phase II, assuming a type I error of 0.05 and power of 0.90, a Fisher's Exact test will detect an increase in IPG therapy of at least 16% at three months after diagnosis. This means that the objective will obtain statistical significance if 52 of 200 SND subjects in Phase II opt for IPG therapy. The Poisson regression for the same scenario has a power of 0.95 to compare IPG incidence of 0.25 versus 0.625 implants per person-year. The power of this objective will improve if the percentage of SND diagnoses is larger than 20%. In order to better account for the proportion of SND diagnosis and IPG adoption per

This document is electronically controlled. Printed copies are considered uncontrolled.

Confidential

geography/country, the Phase II sample size will be recalculated within the geography/country once Phase I data collection is complete.

Stopping Guidelines for Futility

If Phase I of the study suggests that only 5% of enrolled subjects meet an SND indication and that only 5% of those indicated opt for IPG therapy, the study may close for futility at the end of Phase I within that geography/country. Suppose that the percent of SND diagnosis is 5% and that 5% of those indicated will opt for therapy. Assuming 500 subjects in Phase I, 5,440 subjects will be needed in Phase II to see an increase in the implant rate from 5% to 30%. This suggests a scenario with insufficient power to continue into Phase II.

[figure not shown]

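### Co-primary 2 compares raw implant proportions although Phase I implant data close earlier relative to diagnosis, so on a clock from diagnosis the t=6 comparison can be shifted only towards Phase II.

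*Protocol*

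**What the plan says.** **Data cut-offs.** Protocol 4.3 closes Phase I diagnosis and implant data on one date: "collection of diagnostic assessment and implant data will be complete 6 months after the last enrollment for the geography/country". SAP section 5 agrees: once Phase I enrolment ends, "patients will be followed for six months and then will be exited from the study". For Phase I centres that start late or enrol few subjects, Protocol 4.3 has a separate rule: "the subjects will be followed for a maximum of 6 months and exited from the study". Phase II differs: "Collection of implant data will be complete 6 months after the last Phase II diagnosis for the respective geography/country".

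**Endpoint.** SAP 4.1.2.1 sets the proportion at "time point t where t= 3, 6, and any additional 3-month interval for which there is sufficient follow-up information". In SAP 8.5.2.1 part B (and Protocol 11.1) the numerator is subjects with an IPG by t, and "the number of subjects with an SND diagnosis will be included in the denominator". No minimum follow-up per subject is required.

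**Clock.** Part B says only that estimates are "based on information from fixed time points at 3 months of follow-up, 6 months of follow-up". The power text in SAP 8.5.2.2 is specific: "IPG therapy will be adopted by 10% of SND subjects at three months after diagnosis". The Poisson offset in SAP 8.5.2.1 also starts at SND diagnosis, and SAP 4.2.3.1 defines time to treatment as implant date minus diagnosis date.

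**Test.** SAP 8.5.2.1 has Fisher's exact test decide significance. SAP section 6 limits all phase comparisons to South Asia.

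**The concern.** Every Phase II subject with a diagnosis has at least 6 months between diagnosis and the implant-data cut-off. A Phase I subject diagnosed near the cut-off may have almost none, yet stays in the denominator and counts as not implanted. If t runs from diagnosis, the cut-off alone can lower the Phase I proportion at t=6 and cannot lower that of Phase II. The error therefore runs in the direction that the study hopes to show. The rule on sufficient follow-up does not prevent this: it is undefined, and it governs which time points are reported, not who is counted. With one geography left in the comparison, no other region can offset an artefact.

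**Working it through.** **1. The plan's own figure.** Inputs (SAP 8.5.2.2): 10% vs 26%, 100 vs 200 SND subjects, alpha 0.05 (two-sided assumed), power 0.90. With r = 2, δ = 0.16 and p̄ = (0.10 + 2×0.26)/3 = 0.2067:

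n' = [1.96·√(3·p̄·q̄) + 1.2816·√(2·0.09 + 0.1924)]² / (2·0.16²) = (1.3746 + 0.7821)²/0.0512 = 90.8.

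With the continuity correction, n = (n'/4)·[1 + √(1 + 6/(n'·2·0.16))]² = 22.71 × 4.403 = 100. The stated 100 vs 200 is reproduced; exact Fisher power is 0.92.

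**2. Model for the cut-off.** Assumptions not in the documents: no true effect, uniform enrolment, constant implant hazard after diagnosis, no losses, late centres left out. Enrolment lasts 12 months in Phase I and 18 in Phase II (Protocol 4.3). The hazard is set to give 10% by 3 months: h = −ln(0.90)/3 = 0.0351 per month.

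- Phase II, all with a full window: 1 − exp(−6h) = 1 − 0.9² = 19.0%.
- Phase I: let W be the time from enrolment to cut-off, uniform on 6 to 18 months, and D the time from enrolment to diagnosis. The proportion by t is 1 − E[exp(−h·min(t, W − D))] over subjects with D < W.

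**3. Even diagnosis.** Take 20% as the total diagnosed, with D uniform on 0 to 6 months. This gives 0.20×500 = 100 and 0.20×1000 = 200, the plan's numbers. The share of Phase I subjects with under 6 months after diagnosis is E[D]/12 = 3/12 = 25%.

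**4. Continuing diagnosis.** Take a constant diagnosis hazard λ = −ln(0.80)/6 = 0.0372 per month.

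- Phase I diagnosed: 1 − (0.8 − 0.512)/(12λ) = 35.5%, about 177 of 500.
- Phase II diagnosed: 1 − (0.8 − 0.4096)/(18λ) = 41.7%, about 417 of 1000.
- Share of diagnosed Phase I subjects with under 6 months after diagnosis: 45.5%.

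**5. Results.** Numerical integration for the proportions; the two-sided Fisher rejection rate was enumerated exactly.

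| Diagnosis timing | Implanted by 3 months | t | Phase I vs II | SND subjects | False positives |
|---|---|---|---|---|---|
| Even over 6 months | 10% | 3 | 9.8% vs 10.0% | 100 vs 200 | 3.9% |
| Even over 6 months | 10% | 6 | 17.5% vs 19.0% | 100 vs 200 | 5.0% |
| Even over 6 months | 26% | 6 | 42.0% vs 45.2% | 100 vs 200 | 7.9% |
| Continuing | 10% | 3 | 9.0% vs 10.0% | 100 vs 200 | 4.4% |
| Continuing | 10% | 3 | 9.0% vs 10.0% | 177 vs 417 | 5.3% |
| Continuing | 10% | 6 | 15.0% vs 19.0% | 100 vs 200 | 11.5% |
| Continuing | 10% | 6 | 15.0% vs 19.0% | 177 vs 417 | 19.6% |

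For reference, equal proportions of 19% give 4.2% at 100 vs 200. With 10-month Phase I enrolment (SAP section 5), the even-diagnosis rates at t=6 become 5.4% (10% implanted) and 9.4% (26% implanted).

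**6. Faster timing at t=6, 10% by 3 months, 100 vs 200.**

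- Diagnosis at a mean of 1 month: 18.9% vs 19.0%, false positives 4.2%.
- Diagnosis at a mean of 3 months: about 17.7% vs 19.0%, under 5%.
- Continuing diagnosis with implants clustered at a mean of 1 month: 9.7% vs 10.5%, about 4%.

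**7. Late or low-enrolling Phase I centres.** At 10 subjects and 20% diagnosed, each adds about 2 SND subjects. If their 6 months run from enrolment, almost none has a 6-month window after diagnosis. The number of such centres is not given.

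**The case against.** **The effect may be nominal.** This is the strongest reply, and it stands in part. The assumption that yields 100 vs 200 is 20% diagnosed in total. Spread evenly over 6 months, that gives about 5% at t=6. A reader might infer that the test runs at 11% or more, or about 30% if 26% are implanted by 3 months, at the planned sample size. The documents do not support that: those rates pair continuing diagnosis with 100 vs 200, whereas continuing diagnosis implies about 177 vs 417. Slow diagnosis is still a case that the plan allows for, since co-primary 1 lists t=12 and SAP 8.5.4.1 tabulates diagnoses out to 12-18 months.

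**The clock is implied.** A reader might infer that the start of t is wholly open, so that the bias could run either way. That is too strong. The power text, the Poisson offset, the rationale for the time points and the time-to-treatment definition all point to diagnosis. Only part B's wording about months of follow-up leaves room for enrolment, which makes this a wording gap.

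**Other analyses allow for follow-up.** SAP 8.5.5.1 plans Kaplan-Meier curves and a log-rank test for time to implant, and SAP 8.5.2.1 adds a Poisson model. Neither corrects the raw proportion that Fisher's test uses. No error in the Poisson model is claimed here.

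**Exploratory status and code.** SAP 4.1 calls the study exploratory, which lowers the stakes; the test of significance remains. The SAP's change log mentions corrected code for exact tests. No such code is visible in the public text, so whether it restricts the analysis set cannot be checked.

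**Conclusion.** The concern holds for t=6, on the clock from diagnosis that most of the text implies. The cut-off rules can then shift the comparison only towards Phase II. With no true effect and 10% implanted by 3 months, the gap is 1.5 points if 20% in total are diagnosed evenly over 6 months. The false-positive rate is then about 5%, or about 8-9% if 26% are implanted by 3 months. The gap is 4 points if diagnosis continues at 20% per 6 months, with a false-positive rate of about 11% at 100 vs 200 and about 20% at 177 vs 417. It is negligible if diagnosis is fast or implants follow it closely. These figures rest on uniform enrolment and a constant implant hazard except where stated. A reader might infer that the whole of co-primary 2 is compromised. It is not: t=3, the powered time point, stays near nominal at the planning rate. This should be fixed; the direction is certain on that clock, while confidence in the size is moderate.

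**What to change.** In SAP 8.5.2.1, state that t runs from SND diagnosis. At each t, compare Kaplan-Meier cumulative implant proportions between phases. Censor at the phase's implant-data cut-off and at death, withdrawal or loss to follow-up. For late or low-enrolling Phase I centres, the cut-off is their own 6-month limit, and the SAP should say when it starts. Keep subjects who exited because they will not be paced as not implanted up to the cut-off; censoring them would overstate the implant proportion.

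As a check, take continuing diagnosis with an assumed loss of 12% a year (the SAP expects 10-15% attrition). The rule as written gives 14.6% vs 18.5% at t=6. Kaplan-Meier gives 19.0% vs 19.1%, with false positives of 4.9%.

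Alternatively, at t=6 and later, apply Fisher's test only to subjects in both phases who were diagnosed at least t months before their cut-off. This drops roughly 25-46% of Phase I SND subjects at t=6 under the two timing models, whereas Kaplan-Meier keeps all of them. The restriction should not extend to t=3: with continuing diagnosis it would leave 79 of 100 Phase I subjects and cut power from 0.92 to 0.87, where no inflation is shown at the planning rate.

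The cost is SAP wording and slightly more analysis work. The diagnosis and implant dates are already needed for Secondary Objective 3.

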11.1 Primary Objective(s)

Primary Objective #1

Evaluate the impact of the intervention on the diagnosis of SND.

Endpoint Definition

The absolute change in the proportion of subjects diagnosed with SND at pre-specified time points ($\% = \text{number diagnosed}/\text{number enrolled} \times 100$ at time point t where $t = 6, 12$, and any additional 6-month interval for which there is sufficient follow-up information) and the absolute change in the number of subjects diagnosed with SND per person-year.

Analysis Methods

A. Statistical Methodology

To compare the proportion of subjects with an SND diagnosis pre-intervention (Phase I) to the proportion post-intervention (Phase II), a chi-square test will determine statistical significance. The proportion of subjects diagnosed will be evaluated at multiple time points because the time to diagnosis is expected to vary by geography. Thus, times are pre-specified starting at 6 months and any additional 6-month interval thereafter for which there is sufficient follow-up data available to compare study phases. Proportions calculated at all available time points will be reported. Additionally a Poisson regression will compare the average number of subjects with an SND diagnosis in Phase I and Phase II where the subject time in study is treated as an offset in the model. The above described tests will be performed separately within geography/country as well as overall.

B. Determination of Patients/Data for Analysis

All subjects that are enrolled in the study will be included in the determination of the proportion estimates. The proportion estimates will be calculated based on information from fixed time points at 6 months of follow-up, 12 months of follow-up, and any additional 6-month interval thereafter for which there is sufficient follow-up data available to compare study phases. The number of subjects that obtain a SND diagnosis by pre-specified time point $t= 6, 12, \text{ etc.}$, is included in the numerator and the number of subjects enrolled is included in the denominator.

Sample Size Methods and Assumptions

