8.5.1.1. Analysis Methods

A. Statistical Methodology

To compare the proportion of subjects with an SND diagnosis pre-intervention (Phase I) to the proportion post-intervention (Phase II), a chi-square test will determine statistical significance. The proportion of subjects diagnosed will be evaluated at multiple time points because the time to diagnosis is expected to vary by geography. Thus, times are pre-specified starting at 6 months and any additional 6-month interval thereafter for which there is sufficient follow-up data available to compare study phases.

Proportions calculated at all available time points will be reported. Additionally a Poisson regression will compare the average number of subjects with an SND diagnosis in Phase I and Phase II where the subject time in study is treated as an offset in the model. The above described tests will be performed only for subjects in the South Asia geographical region as per section 6.

[REDACTED]

[REDACTED]

This document is electronically controlled. Printed copies are considered uncontrolled.

Confidential

[REDACTED]

[REDACTED]

[REDACTED]

B. Determination of Patients/Data for Analysis

All subjects that are enrolled in the study will be included in the determination of the proportion estimates. The proportion estimates will be calculated based on information from fixed time points at 6 months of follow-up, 12 months of follow-up, and any additional 6-month interval thereafter for which there is sufficient follow-up data available to compare study phases. The number of subjects that obtain an SND diagnosis by pre-specified time point $t = 6, 12, \text{ etc.}$, is included in the numerator and the number of subjects enrolled is included in the denominator.

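### Primary Objective 1: the 12-month diagnosis proportion divides by all enrolled subjects although planned follow-up is shorter in Phase I, so the chi-square comparison leans towards Phase II

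*Protocol*

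**What the plan says.** **Endpoint and test.** Protocol 11.1 and SAP 4.1.1.1 define the diagnosis proportion at 6 months, 12 months and any further 6-month point with sufficient follow-up, a term neither document defines. A chi-square test between phases decides significance.

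**Denominator.** Protocol 11.1: "All subjects that are enrolled in the study will be included in the determination of the proportion estimates". In SAP 8.5.1.1 B the number diagnosed by time t "is included in the numerator and the number of subjects enrolled is included in the denominator". No rule limits the denominator at 12 months or later to subjects who could be observed that long.

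**Phase I follow-up.** Protocol 4.3: "Enrollment for Phase I is anticipated to occur for approximately 12 months but will continue until 550 subjects have been enrolled", and "collection of diagnostic assessment and implant data will be complete 6 months after the last enrollment for the geography/country". SAP section 5 agrees: once enrolment in a region is complete, "patients will be followed for six months and then will be exited from the study". Centers that start late, or have fewer than 10 subjects when Phase I enrolment stops, go on to 10 subjects; then "the subjects will be followed for a maximum of 6 months and exited from the study".

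**Phase II follow-up.** Protocol 4.3: "Enrollment during this phase is anticipated to occur for approximately 18 months per geography/country", and "For subjects enrolled during Phase II collection of diagnostic assessment data will be complete 6 months after last enrollment for the geography/country". SAP section 5 instead plans Phase II enrolment for twice as long as Phase I, with 10 months of Phase I as its worked case.

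**The concern.** Each phase closes on a calendar date 6 months after its last enrolment, so a subject's follow-up depends on when in the phase that subject enrolled. A longer enrolment period gives longer average follow-up. Phase II is planned to enrol for longer, so more of its subjects can be observed to month 12.

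A subject exited administratively at month 8 cannot be recorded as diagnosed at month 11, yet stays in the 12-month denominator as not diagnosed. Phase I has more such subjects. If diagnoses continue after month 6, the Phase I proportion is understated by more than the Phase II proportion, and the difference looks like an intervention effect. Twelve months is named outright in the primary endpoint, so this affects a planned primary comparison.

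**Working it through.** **1. The plan's own figure.** With 500 v 1000 subjects, 20% v 28% and two-sided alpha 0.05 (sidedness is not stated), chi-square power is 0.928, or 0.918 with continuity correction. The smallest difference with 90% power is 7.6 points (7.7-7.8 corrected). The stated 8 points is reproduced. That calculation concerns month 6 only.

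**2. Who can reach month 12.** Assume uniform enrolment over A months and close-out 6 months after the last enrolment. Follow-up then runs from 6 to 6 + A months, and the share able to reach month 12 is (A - 6)/A.

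| Enrolment, Phase I / II | Follow-up (months) | Share reaching 12 months |
|---|---|---|
| Protocol: 12 / 18 months | 6-18 v 6-24 | 6/12 = 50% v 12/18 = 67% |
| SAP: 10 / 20 months | 6-16 v 6-26 | 4/10 = 40% v 14/20 = 70% |

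All subjects reach month 6. For month 18 the share is (A - 12)/A: 0% v 33% on Protocol enrolment.

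**3. Recorded proportion with no effect, constant hazard.** Use the same hazard in both phases, set by the plan's 20% at 6 months: h = -ln(0.8)/6 = 0.0372 per month.

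- True 12-month value: F(12) = 1 - 0.8² = 36.0%.
- Average recorded value for subjects whose follow-up ends between 6 and 12 months: 1 - (0.80 - 0.64)/(6h) = 1 - 0.16/0.2231 = 28.3%.
- Recorded proportion = share × 36.0% + (1 - share) × 28.3%.

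| Enrolment | Phase I | Phase II | Gap | Rejection rate, 550 v 1100 |
|---|---|---|---|---|
| 12 / 18 | 32.15% | 33.43% | (0.667 - 0.50) × 7.70 = +1.3 points | 8% |
| 10 / 20 | 31.38% | 33.69% | (0.70 - 0.40) × 7.70 = +2.3 points | 15% |

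The rejection rate is for the two-sided chi-square by normal approximation; the nominal value is 5%.

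**4. If diagnoses level off.** Take F(x) = P(1 - exp(-kx)), with k chosen so that F(6) = 20%.

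| Plateau P | F(12) | Gap, 12 / 18 | Gap, 10 / 20 |
|---|---|---|---|
| 25% | 24.0% | +0.2 points (5%) | +0.4 points (5%) |
| 40% | 30.0% | +0.7 points (6%) | +1.3 points (9%) |

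**5. Length of Phase I enrolment.** Phase I continues until 550 are enrolled and may run past 12 months. With Phase II at 18 months and a constant hazard, 15 months of Phase I gives a gap of +0.5 points. Eighteen months gives zero.

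**6. Catch-up centers.** Suppose the 6-month maximum ran from each subject's own enrolment and 10% of Phase I were at such centers (an assumption). The Phase I value on 12 / 18 enrolment would be 0.9 × 32.15% + 0.1 × 20% = 30.9%, and the gap +2.5 points (17%). This depends on a starting date that the text does not give.

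**7. After correction.** With a constant hazard, a follow-up-aware estimate gives 36.0% in both phases at month 12. The gap is zero and the test keeps its 5% level.

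**The case against.** **Other analyses already allow for follow-up.** Diagnoses per person-year is part of the same primary endpoint and is tested by Poisson regression with time in study as an offset. Secondary Objective 2 uses Kaplan-Meier curves and a log-rank test. SAP 4.1 also calls the study exploratory. This stands as mitigation, since a reader would see the analyses disagree. It does not correct the proportions, and the chi-square on those proportions is the test said to decide significance.

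**The size depends on the diagnosis curve.** This stands. Subjects found to have no SND indication may be exited (Protocol 5.7, SAP section 5), which argues against a constant hazard over everyone enrolled. An early plateau makes the bias small.

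**A reader might infer that catch-up centers cap Phase I subjects at 6 months and so can never supply a 12-month diagnosis.** The text does not establish this. The rule takes effect after Phase I enrolment has stopped, when a low-enrolling center's earlier subjects may already have more than 6 months. The more natural reading runs the 6 months from the center's own enrolment stop, in parallel with the ordinary rule.

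**A reader might also take month 18 as the main damage.** The same arithmetic gives 35.5% v 39.9% there (+4.4 points, 42% rejection). But later time points are used only where follow-up suffices to compare phases. On the Protocol's own timetable no Phase I subject exceeds 18 months, so that condition, though undefined, should rule the comparison out.

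**Conclusion.** The concern holds for month 12, at modest size. With equal diagnosis hazards in the two phases, the planned 12-month chi-square favors Phase II whenever diagnoses continue after month 6 and Phase II enrols for longer. With no true effect the gap is +1.3 points (8% false positives) on Protocol enrolment and +2.3 points (15%) on SAP enrolment under a constant hazard. With a plateau at 25-40% it is 0.2-0.7 points (5-6%) and 0.4-1.3 points (5-9%) respectively. These figures assume uniform enrolment, 20% diagnosed at 6 months and 550 v 1100 subjects. The documents give no diagnosis curve beyond month 6.

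It would be too strong to say that the Phase II proportion must rise without an effect: with an early plateau or slower Phase I enrolment the bias is negligible. The 6-month comparison that carries the power calculation is unbiased provided each subject gets a full 6 months. Restricting phase comparisons to South Asia (SAP section 6) does not change the mechanism.

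**What to change.** In SAP 8.5.1.1, with matching wording in Protocol 11.1, change the rule for t of 12 months or more:

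- **Preferred:** compare Kaplan-Meier (cumulative incidence) estimates at t between phases, censoring at the planned administrative cut-off. Keep subjects exited as not SND-indicated as non-diagnosed; do not censor them at exit.
- **Alternative:** include a subject at t only if the planned cut-off for that subject's phase and center is at least t months after enrolment. Base this on enrolment date, not on actual exit.
- **Define sufficient follow-up:** a time point qualifies only if both phases have subjects whose planned follow-up reaches t.

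State the date from which the catch-up centers' 6-month maximum was counted, since it sets those subjects' planned cut-off. Changing Phase I follow-up itself is no longer possible: SAP section 6 records Phase I as complete.

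The cost is SAP and Protocol wording plus one derived variable, planned cut-off minus enrolment date. Intervals at month 12 become wider. On 12-month enrolment the restriction drops about half of Phase I (275 of 550), while Kaplan-Meier keeps everyone. The 18-month phase comparison is lost. The 6-month analysis is unchanged.
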